#### **4.5. Criteria for Temporarily Delaying Vaccine Administration**

The following conditions are temporary or self-limiting and a subject may be vaccinated once the condition(s) has/have resolved and no other exclusion criteria are met:

1. Current febrile illness (oral temperature of  $\geq 100.4^{\circ}\text{F}$  [ $38.0^{\circ}\text{C}$ ]) or other acute illness within 48 hours prior to investigational product administration.

2. Subject has received licensed nonlive influenza vaccine within the previous 14 days or any other vaccine within the previous 28 days before investigational product administration.
3. Subject has received systemic antibiotic therapy for an acute illness within 72 hours before the study vaccination.
4. If systemic corticosteroids have been administered short term (<7 days) for treatment of an acute illness, investigational product administration should be delayed until systemic corticosteroid use has been discontinued for at least 1 month. Inhaled, intra-articular/intrabursal, or topical corticosteroids are permitted.

If a subject meets any delay criteria for vaccination, all study procedures, including blood sample collection relating to that visit, should be delayed until the day of vaccination.

#### **4.6. Lifestyle Guidelines**

All male subjects who are able to father children and are sexually active must agree to use a highly effective method of contraception consistently and correctly from the signing of the ICD to 28 days after the last dose of investigational product. The investigator or his or her designee, in consultation with the subject, will select an appropriate method of contraception for the individual subject and his partner from the permitted list of contraception methods (see below), and instruct the subject in its consistent and correct use. Subjects need to affirm that they meet the criteria for correct use of at least 1 of the selected methods of contraception. The investigator or his or her designee, at each study visit, will confirm and document consistent and correct use and document such conversation in the subject's chart. In addition, the investigator or his or her designee will instruct the subject to call immediately if the selected contraception method is discontinued or if pregnancy in his partner is known or suspected.

Highly effective methods of contraception are those that, alone or in combination, result in a failure rate of less than 1% per year when used consistently and correctly (ie, perfect use) and include the following:

1. Established use of oral, inserted, injected, implanted, or transdermal hormonal methods of contraception is allowed provided the subject's partner remains on the same treatment throughout the entire study and has been using that hormonal contraceptive for an adequate period of time to ensure effectiveness.
2. Correctly placed copper-containing intrauterine device (IUD).
3. Male condom or female condom used WITH a spermicide (ie, foam, gel, film, cream, suppository).
4. Male sterilization with absence of sperm in the postvasectomy ejaculate.

5. Bilateral tubal ligation, bilateral salpingectomy, or bilateral tubal occlusive procedure (provided that occlusion has been confirmed in accordance with the device's label).
6. Female partner who meets the criteria for nonchildbearing potential, as described below:
  - Have undergone a documented hysterectomy and/or bilateral oophorectomy;
  - Have medically confirmed ovarian failure; or
  - Achieved postmenopausal status, defined as follows: cessation of regular menses for at least 12 consecutive months with no alternative pathological or physiological cause.

#### **4.7. Sponsor's Qualified Medical Personnel**

The contact information for the sponsor's appropriately qualified medical personnel for the trial is documented in the SRM.

To facilitate access to appropriately qualified medical personnel on study-related medical questions or problems, subjects are provided with a contact card. The contact card contains, at a minimum, protocol and investigational compound identifiers, subject study number, contact information for the investigational site, and contact details for a contact center in the event that the investigational site staff cannot be reached to provide advice on a medical question or problem originating from another healthcare professional not involved in the subject's participation in the study. The contact number can also be used by investigational staff if they are seeking advice on medical questions or problems; however, it should only be used in the event that the established communication pathways between the investigational site and the study team are not available. It is therefore intended to augment, but not replace, the established communication pathways between the investigational site and study team for advice on medical questions or problems that may arise during the study. The contact center number is not intended for use by the subject directly, and if a subject calls that number, he or she will be directed back to the investigational site.

### **5. STUDY TREATMENTS**

For the purposes of this study, and per International Council for Harmonisation (ICH) guidelines, investigational product is defined as a pharmaceutical form of an active ingredient or placebo being tested or used as a reference in a clinical trial, including a product with a marketing authorization when used or assembled (formulated or packaged) in a way different from the approved form, or when used for an unapproved indication, or when used to gain further information about an approved use (ICH E6 1.33).

#### **5.1. Allocation to Investigational Product**

Allocation of subjects to vaccine groups (at both entry to the study and entry in the extension stage) will proceed through the use of the interactive response technology (IRT) system that is accessible 24 hours a day, 365 days a year. Specific instructions for use of the IRT system will be provided under separate cover. The study site will obtain the subject's randomization

number and container number (or equivalent) assignment from the IRT system. The randomization number and the date on which the randomization number was assigned will be recorded on the case report form (CRF). Once subject numbers, container numbers, and randomization numbers have been assigned, they cannot be reassigned.

## **5.2. Blinding of Site Personnel**

In this observer-blinded study, the study staff dispensing and administering the vaccine will be unblinded, but all other site study personnel, including the principal investigator and the subject, will be blinded during the vaccination periods of the study.

Following the third interim analysis (when Month 7 [after the first dose] data are available from all continuing subjects), site personnel will be unblinded to vaccine assignments for the first 3 doses. This will enable site personnel to identify subjects eligible to enter the extension stage. During the extension stage, site personnel (excluding the study staff dispensing and administering the vaccine) will be blinded to vaccine allocation at the fourth dose until Visit 12 (6 months after the fourth dose).

The principal investigator will assign the responsibility of unblinded dispenser and unblinded administrator to persons who will not participate in the evaluation of any study subject. More than 1 unblinded dispenser/administrator may be assigned per site. A member of the study site staff or clinic pharmacy should fulfill this role. Contact between the unblinded dispenser and study subjects should be kept to a minimum. The investigator, study coordinator, and any site staff other than the unblinded dispenser/administrator must not be allowed to know the investigational product assigned to any study subject and must not be allowed to see the investigational product container contents.

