### 2.2.2. Primary Safety Endpoints

- Numbers and proportions of subjects reporting local reactions (pain, erythema, and induration) and their severity, as self-reported on e-diaries for up to 14 days following Vaccinations 1, 2, and 3.
- Numbers and proportions of subjects reporting systemic events (fever, vomiting, diarrhea, headache, fatigue, new or worsening muscle pain, and new or worsening joint pain) and their severity, as self-reported on e-diaries for up to 14 days following Vaccinations 1, 2, and 3.
- Numbers and proportions of subjects reporting AEs from the first vaccination up to 28 days after the third vaccination categorized according to the Medical Dictionary for Regulatory Activities (MedDRA).
- Numbers and proportions of subjects reporting SAEs from the first vaccination until 6 months after the third dose of vaccine, categorized according to MedDRA.

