### **8.2. Reporting Period**

For SAEs, the active reporting period to Pfizer or its designated representative begins from the time that the subject provides informed consent, which is obtained prior to the subject's participation in the study, ie, prior to undergoing any study-related procedure and/or receiving investigational product, through and including Visit 8 (Month 7 for subjects on the Day 1, 8, and 30 regimen and Month 12 for subjects on the Month 0, 1, and 6 regimen).

During the extension stage, the active reporting period for SAEs to Pfizer or its designated representative begins from the time that the subject provides informed consent for the extension stage, which is obtained prior to the subject's participation in the extension stage, ie, prior to undergoing any study-related procedure and/or receiving investigational product, through and including Visit 12 (6 months after the fourth dose).

SAEs occurring to a subject after the active reporting period has ended should be reported to the sponsor if the investigator becomes aware of them; at a minimum, all SAEs that the investigator believes have at least a reasonable possibility of being related to investigational product are to be reported to the sponsor.

All AEs should be recorded on the CRF from the time the subject provides informed consent until 1 month after the third vaccination (Visit 6 [Month 2] for subjects on the Day 1, 8, and 30 regimen and Visit 7 [Month 7] for subjects on the Month 0, 1, and 6 regimen).

During the extension stage, all AEs should be recorded on the CRF from the time the subject provides informed consent until 1 month after the fourth vaccination (Visit 11).

Any AE occurring up to 48 hours after each subsequent blood draw (Visit 6 [Month 2], Visit 7 [Month 4], Visit 8 [Month 7], and Visit 9 [Month 13] for subjects on the Day 1, 8, and 30 regimen and Visit 7 [Month 7], Visit 8 [Month 12], and Visit 9 [Month 18] for subjects on the Month 0, 1, and 6 regimen) must be recorded on the CRF.

During the latter part of the extension stage, any AE (including RRIs) occurring up to 48 hours after the blood draw at Visits 12, 13, 14, 15, 16, and 17 (Months 6, 12, 18, 24, 30, and 36 after the fourth dose) must be recorded on the CRF.

The investigator is required to assess whether the AE may be related to the subject's participation in the study.

CCI

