#### **9.4.3. Third Interim Analysis**

The third interim analysis is planned for the study when Month 7 data are available from all continuing subjects. All available immunogenicity and safety data will be included in this analysis.

The objective of the third analysis is to determine the suitability of the Month 0, 1, and 6 regimen for further study and to select the optimal vaccine dose level for further study.

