### **6.1.2. Primary Safety Endpoints**

**Endpoints:** Primary safety endpoints in [Section 3.1.2](#)

- Analysis time points:  
Local reactions and systemic events: Up to 14 days following each vaccination  
AEs: From the first vaccination up to 28 days after the third vaccination  
SAEs: From the first vaccination until 6 months after the third vaccination
- Analysis population: Safety population
- Analysis methodology: Descriptive; see [Section 5.2.1](#)
- Supporting objective: Primary safety objective

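### Month 0, 1, 6 regimen: sites may learn the Doses 1-3 allocation after the third interim (Month 7 data), before the primary SAE window closes at Month 12

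*Protocol*

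**What the plan says.** **Extent of site blinding.** Under Protocol 5.2 the subject and all site staff other than those who dispense and administer vaccine "will be blinded during the vaccination periods of the study".

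**Release of Doses 1-3.** The same section continues: "Following the third interim analysis (when Month 7 [after the first dose] data are available from all continuing subjects), site personnel will be unblinded". What is disclosed is the allocation at Doses 1-3. The reason given is: "This will enable site personnel to identify subjects eligible to enter the extension stage". Protocol 9.4.3 gives the same trigger: "The third interim analysis is planned for the study when Month 7 data are available from all continuing subjects". Protocol 5.4 gives sites access through the IRT at the appropriate time, with no condition at subject level.

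**SAE window.** The primary safety endpoint in Protocol 2.2.2 counts subjects with "SAEs from the first vaccination until 6 months after the third dose of vaccine", and SAP 6.1.2 agrees: "SAEs: From the first vaccination until 6 months after the third vaccination". For active SAE reporting Protocol 8.2 gives this period, where the later date belongs to the Month 0, 1, 6 regimen: "through and including Visit 8 (Month 7 for subjects on the Day 1, 8, and 30 regimen and Month 12 for subjects on the".

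**Dose 4.** In the extension, Protocol 5.2 says that site personnel, apart from the unblinded dispensers and administrators, "will be blinded to vaccine allocation at the fourth dose until Visit 12 (6 months after the fourth dose"). Under 8.2 that visit is also where active SAE reporting for the extension ends.

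**The concern.** In the Day 1, 8, 30 regimen, Month 7 is the visit six months after Dose 3, so its SAE window has closed when the third interim is triggered. For Dose 4 the site blind lasts until active SAE reporting ends. Only the Month 0, 1, 6 regimen lacks this alignment: the trigger uses Month 7 data, while its SAE window stays open to Month 12.

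At Visit 8 (Protocol 6.2.8) the investigator decides from clinical evaluation whether SAEs have occurred since the previous visit. Whether an important medical event counts as serious is a matter of judgement (8.6). Staff who know the allocation might question subjects or classify events differently for vaccine and placebo. What is at stake is the late part of one primary safety endpoint in one regimen, which has about 61 placebo subjects.

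**Working it through.** **1. Check of the plan's own figure.** Protocol 3.2 gives about 18 months of participation in the Month 0, 1, 6 regimen. Adding the visit windows for Visits 2, 5 and 9: (25 to 35) + (135 to 165) + (340 to 380) = 500 to 580 days, or 16.4 to 19.1 months. The midpoint is 540 days (17.7 months), so the stated figure is reproduced.

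**2. Gap for one subject.** Visit 7 is 25 to 35 days and Visit 8 is 165 to 195 days after Dose 3. The gap is 165 - 35 = 130 to 195 - 25 = 170 days, nominally 150 days or about 5 months.

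**3. Accrual (assumed).** Protocol 3.3 gives about 21 months for the original portion. 21 - 18 = about 3 months of enrolment. Both inputs are approximate.

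**4. Overlap.** Time is counted in months from first entry. The last Month 7 visit is at 3 + 7 = 10. With lag L for assays, cleaning and analysis, unblinding is at 10 + L. A subject entering at month e closes the SAE window at 12 + e. So

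overlap = max(0, 12 + e - (10 + L)) = max(0, 2 + e - L), with e taken as uniform on 0 to 3.

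The mean is 3.5 - L for L up to 2, and (5 - L)²/6 for L from 2 to 5. Person-years are 427 (183 + 183 + 61) times the mean, divided by 12, without dropout. The last column uses nominal Month 13 for Visit 9 of the Day 1, 8, 30 regimen.

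| Lag L (months) | Month-regimen subjects still in SAE window | Mean overlap (months) | Maximum (months) | Person-years (placebo) | Day-regimen subjects past Visit 9 |
|---|---|---|---|---|---|
| 0 | 100% | 3.5 | 5 | 124.5 (17.8) | 0% |
| 1 | 100% | 2.5 | 4 | 89.0 (12.7) | 0% |
| 2 | 100% | 1.5 | 3 | 53.4 (7.6) | 0% |
| 3 | 67% | 0.67 | 2 | 23.7 (3.4) | 0% |
| 4 | 33% | 0.17 | 1 | 5.9 (0.8) | 33% |
| 5 | 0% | 0 | 0 | 0 | 67% |

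At lags 2, 3 and 4 the mean is 12.5%, 5.6% and 1.4% of the 12-month window. The maximum is that of the last subject entered, 12 - 7 - L = 5 - L, and does not depend on accrual; the mean does. With 6 months of accrual the mean is 2.1, 0.75 and 0.08 months at lags 0, 2 and 4.

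**5. What the Visit 9 provisions suggest about the lag.** Protocol 4.4 (criterion 2), 6.1.9 and 6.2.9 allow for subjects who reach Visit 9 before unblinding. The earliest such visit in the Day 1, 8, 30 regimen is day 7 + 20 + 340 = 367 (12.1 months), nominally Month 13. Unblinding then gives a mean overlap of 1.44 or 0.67 months. Unblinding as late as the first Month-regimen Visit 9 (day 500, 16.4 months) gives none.

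**6. Number of events.** The documents give no SAE rate. At an assumed 5 to 15 SAEs per 100 person-years, the overlap would contain 2.7 to 8.0 SAEs at lag 2 (placebo 0.4 to 1.1), 1.2 to 3.6 at lag 3 (placebo 0.2 to 0.5) and 0.3 to 0.9 at lag 4. At lag 0, the upper bound, it would contain 6.2 to 18.7 (placebo 0.9 to 2.7). These are all SAEs in the overlap, not events misreported because of unblinding.

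**The case against.** The release is a declared choice. A reader might infer that the protocol breaks its own blinding rule, but 5.2 promises site blinding only during the vaccination periods and states why the allocation is released. Section 5.2 also ends with an undated sentence that investigators must not know the assigned product. Because the same section provides for the release, that sentence neither forbids it nor delays it to Visit 8. The parallel with Dose 4 is imperfect too: the Doses 1-3 allocation decides eligibility for the extension, whereas the Dose 4 allocation decides nothing later. All of this stands.

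Little depends on the endpoint. It is descriptive, reported per vaccine group with a confidence interval, and most SAE criteria are hard outcomes. Subjects are told to report significant illness or hospitalization at once, and sites must notify SAEs within 24 hours, so events reported before unblinding are unaffected. The documents do not say that subjects are told their allocation at that point, so their own reports may still come from blinded subjects. These facts limit the exposure but do not remove it.

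The overlap may be nil, and the Visit 9 provisions could be read as showing that it is short. Neither can be concluded: those provisions may be contingency wording, and no lag is stated. A lag long enough to remove the overlap (about 5 months) would put about 67% of Day-regimen subjects past Visit 9 and so outside the extension.

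The point may also be too late for prevention. The current text, Amendment 2, adds a Visit 12 blood draw for extension subjects in the month regimen, which suggests that unblinding may already have taken place. No enrolment dates are given, so this is only an inference.

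**Conclusion.** The gap exists: the trigger precedes Month 12, and nothing in Protocol 5.2, 5.4, 6.1.9 or 6.2.9 holds a Month-regimen subject's allocation until Visit 8. Its length cannot be settled from the documents. The range of about 0 to 5 months per subject rests on nominal visit times and an unstated lag; the means also rest on 3 months of uniform accrual.

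A reader might infer that the primary safety data as a whole, or the immunogenicity results, are compromised. The documents do not support that. E-diary data, AEs to 28 days after Dose 3 and the primary antibody draw are collected by Month 7, assay staff stay blinded throughout (5.3), SAE counts do not depend on causality, and there is no hypothesis test. What remains is a possible, small ascertainment bias in late SAEs in one regimen. This is a low-priority recommendation, justified by the low cost of the remedy rather than by a large expected effect.

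**What to change.** **If sites are still blinded.** In Protocol 5.2 and 5.4, leave the planned release unchanged for the Day 1, 8, 30 regimen. For the Month 0, 1, 6 regimen, let the IRT release each subject's Doses 1-3 allocation after the third interim and only once that subject's Visit 8 safety data are entered. If Visit 8 is missed, release it once the 195-day window has closed. Align the study-level unblinding wording in 6.2.9. Emergency unblinding is unchanged.

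Sites can still identify extension candidates. In-window Visits 8 and 9 are at least 340 - 195 = 145 days apart, so release before Visit 9 is normally feasible. That is a visit-to-visit minimum, not a guaranteed margin: data entry shortens it (30 days, for illustration, leaves 115), and the rule also waits for the third interim.

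**If unblinding has occurred.** Record its date, list Month-regimen SAEs by onset before and after it under SAP 6.1.2, and state the limitation. A listing is enough, because the expected number of events is too small for a comparison.

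**Cost.** A regimen-specific IRT rule, a short amendment with IRB/EC approval, and later site access to Month-regimen allocations. The change does not cover the sponsor study team, which is unblinded at the third interim (5.3) while the sponsor may still reclassify a nonserious AE as serious (8.1).

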## **5.3. Blinding of the Sponsor**

Those study team members who are involved in ensuring that protocol requirements for investigational product handling, allocation, and administration are fulfilled at the site will be unblinded for the duration of the study. All other study team members will remain blinded to vaccine assigned/received at Doses 1, 2, and 3 until the third interim analysis. Those study team members will also be blinded to vaccine assigned/received at Dose 4 until Visit 12 (6 months after the fourth dose). Laboratory personnel performing the immunologic assays will remain blinded to vaccine assigned/received throughout the study. Certain sponsor personnel not involved in the conduct of the study will review unblinded data as defined in an internal review committee (IRC) charter per Pfizer standard operating procedures (SOPs). In addition to the IRC members, an unblinded statistician, an unblinded physician, and an unblinded clinical scientist, who are not part of the study team, will be assigned to work with an external independent statistical center supporting the IRC and external data monitoring committee (E-DMC) review activities.

## **5.4. Breaking the Blind**

At the initiation of the study, each study site will be instructed on the method for breaking the blind. The method will be either a manual or electronic process. Blinding codes should only be broken in emergency situations for reasons of subject safety. Whenever possible, the

investigator or subinvestigator consults with a member of the study team prior to breaking the blind. If this is not possible within the time frame required for breaking the blind, a member of the study team should be contacted as soon as possible afterwards. The breaking of the blind will be recorded in the appropriate section of the CRF.

At the appropriate time points for unblinding, site personnel will be able to access subject vaccine allocations for Doses 1, 2, and 3 and Dose 4 using the IRT system.

## **5.5. Vaccine Supplies**

### **5.5.1. Formulation and Packaging**

#### **5.5.1.1. *Clostridium difficile* Vaccine**

CCI

#### **5.5.1.2. Placebo**

The placebo will consist of a sterile normal saline solution for injection (0.9% sodium chloride injection, in a 0.5-mL dose) and will be provided by the sponsor to each study site. The placebo will be packaged within cartons labeled by Pfizer or its designee in accordance with current guidelines and applicable local and legal regulatory requirements. Blinded, sealed cartons will contain 1 single-use 2-mL vial of placebo. Refer to the DAI for details regarding the preparation and dispensing of placebo.

